5.3 Efficacy Assessments

Assessment of extracranial disease (by CT scan or other approved modalities) and intracranial disease (by MRI scan) will be performed per the schedule above and using criteria in Appendix 5. Investigators may obtain more frequent follow-up MRI scans as medically indicated. Baseline assessments should be performed within 28 days prior to first dose of study drug utilizing CT or MRI for systemic lesions and within 28 days for brain lesions (MRI only). In addition to chest, abdomen, pelvis, and brain, all known sites of disease should be assessed at baseline. Subsequent assessments should include chest, abdomen, pelvis, brain, and all known sites of disease and should use the same imaging method as was used at baseline. Participants will be evaluated for tumor response beginning at 12 weeks (\pm 7 days) and every 12 weeks (\pm 7 days) thereafter, until disease progression is documented, or treatment is discontinued (whichever occurs later).

For extracranial disease assessment, contrast-enhanced computed tomography (CT) scans acquired on dedicated CT equipment is preferred for this study. CT with contrast of the chest, abdomen and pelvis and other areas of disease are to be performed for tumor assessments as above. Should a subject have a contraindication for CT IV contrast, a non-contrast CT of the chest and a contrast enhanced MRI of the abdomen and pelvis may be obtained. MRI's should be acquired with slice thickness of <5 mm with no gap (contiguous). Use of CT component of a PET/CT scanner: Combined modality scanning such as with FDGPET/CT is increasingly used in clinical care and is a modality/technology that is in rapid evolution; therefore, the recommendations outlined here may change rather quickly with time. At present, low dose or attenuation correction CT portions of a combined FDG-PET/CT are of limited use in anatomically based efficacy assessments and it is therefore suggested that they should not be substituted for dedicated diagnostic contrast enhanced CT scans for anatomically based RECIST measurements. However, if a site can document that the CT performed as part of a FDGPET/CT is of identical diagnostic quality to a diagnostic CT (with IV and oral contrast) then the CT portion of the FDG-PET/CT can be used for RECIST 1.1 measurements. Note, however, that the FDG-PET portion of the CT introduces additional data which may bias an investigator if it is not routinely or serially performed.

MRI scans: Bi-dimensional and three-dimensional contrast enhanced MRI of the brain will be acquired. Every attempt should be made to image each subject using an identical acquisition protocol on the same scanner for all imaging time points. Cases of suspected radiologic disease progression will be confirmed by an MRI performed at least 4 weeks after the initial radiological assessment of progression.

5.3.1 Confirmation of scans

Verification of Response: Confirmation of intracranial response will be confirmed by an MRI performed at least 4 weeks after the initial radiological assessment per investigator discretion or SOC. If repeat scans confirm overall response (OR), then response should be declared using the date of the initial scan. If repeat scans do not confirm OR, then the subject is considered not to have had an OR.

Verification of Progression: Progression of disease should be verified in cases where progression is equivocal and will be confirmed by a CT or MRI performed at least 4 weeks after the initial radiological assessment of progression per investigator discretion or SOC. If repeat scans confirm PD, then progression should be declared using the date of the initial scan. If repeat scans do not confirm PD, then the subject is considered not to have progressive disease.

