Phase II will take the RP2R schedule from Phase I and apply it to patients who may derive the most benefit from triple or quadruple therapy: Group 1) symptomatic brain metastases [up to 30 patients] and Group 2) LDH > 1x ULN with liver metastases OR bulky visceral disease (sum of longest diameter (SLD) > 44 mm) [up to 60 patients when combined with Group1].

Schema

Enrolled participants will be evaluated for safety and efficacy throughout the study and during follow up at the time points indicated on the time and events schedules presented in Tables 5.2.1 – 5.2.3. Response to treatment will be assessed in the intracranial (Group 1) and extracranial compartments (Group 2) and will be evaluated by serial radiographic assessment every 12 weeks until documented progression, withdrawal of consent, or the end of the study.

Follow-up Phase for each enrolled subject begins when the decision to discontinue a subject from study therapy is made (no further treatment with study therapy).

Participants will be followed for efficacy and OS. Treatment decisions will be based on local imaging evaluations using RANO-BM for intracranial lesions and RECIST 1.1 for extracranial lesions^{69,70}.

Additional imaging may be performed for patient care at the discretion of the investigator. All efficacy objectives will be based on Investigator assessment at the study site.

Safety will be evaluated for all treated participants using the NCI CTCAE version 5.0. Safety assessments will be based on medical review of AE reports, vital sign measurement results, physical examinations, and clinical laboratory tests.

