SD	Non-PD or Not Evaluated	No	SD
Not all evaluated	Non-PD	No	Not Evaluable
PD	Any	Yes or No	PD
Any	PD	Yes or No	PD
Any	Any	Yes	PD

5.7a MISSING ASSESSMENTS AND INEVALUABLE DESIGNATION

When no imaging/measurement is done at all at a particular time point, the patient is not evaluable (NE) at that time point. If only a subset of lesion measurements are made at an assessment, usually the case is also considered NE at that time point, unless a convincing argument can be made that the contribution of the individual missing lesion(s) would not change the assigned time point response. This would be most likely to happen in the case of PD.

5.8a BEST OVERALL RESPONSE: ALL TIMEPOINTS

Best response determination in trials where confirmation of complete or partial response IS required: Complete or partial responses may be claimed only if the criteria for each are met at a subsequent time point as specified in the protocol. In this circumstance, the best overall response can be interpreted as below:

Overall Response First Timepoint	Overall Response Subsequent Timepoint	Best Overall Response
CR	CR	CR
CR	PR	SD, PD, or PR
CR	SD	SD provided minimum criteria for SD duration met, otherwise, PD

CR	PD	SD provided minimum criteria for SD duration met, otherwise, PD
CR	NE	SD provided minimum criteria for SD duration met, otherwise, NE
PR	CR	PR
PR	PR	PR
PR	SD	SD
PR	PD	SD provided minimum criteria for SD duration met, otherwise, PD
PR	NE	SD provided minimum criteria for SD duration met, otherwise, NE
NE	NE	NE

CR = complete response, PR = partial response, SD = stable disease, PD = progressive disease, and NE = not evaluable

5.9a SPECIAL NOTES ON RESPONSE ASSESSMENT

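### The confirmatory scan for intracranial response is discretionary, a failed rescan cancels the response, and a response never rescanned has no counting rule

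*Combined protocol and SAP*

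**What the plan says.** Section 5.3.1 says that intracranial response will be confirmed by an MRI "performed at least 4 weeks after the initial radiological assessment per investigator discretion or SOC". Two consequences follow. If the repeat scan agrees, "If repeat scans confirm overall response (OR), then response should be declared using the date of the initial scan". If it does not, "If repeat scans do not confirm OR, then the subject is considered not to have had an OR". No sentence covers a patient whose first-scan response is never rechecked, and Section 5.3.1 has no matching rule for extracranial response.

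Appendix 5 (5.8a) gives a best-response table under the heading "Best response determination in trials where confirmation of complete or partial response IS required". It adds: "Complete or partial responses may be claimed only if the criteria for each are met at a subsequent time point as specified in the protocol". Under that table, a PR followed by a non-evaluable time point becomes SD if the minimum SD duration is met, and otherwise NE.

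Sections 8.2 and 8.4 define objective response as CR or PR among evaluable patients and do not say whether it must be confirmed. Section 3.1 assesses Group 1 in the intracranial compartment and Group 2 in the extracranial one, and adds: "All efficacy objectives will be based on Investigator assessment at the study site". On timing, Section 5.3 says "Participants will be evaluated for tumor response beginning at 12 weeks", then every 12 weeks with the brain included, and allows more frequent MRI when medically indicated. It does not name the next scheduled scan as the confirmatory one.

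**The concern.** The first half of the rule makes the repeat scan optional. The second half gives a repeat scan the power to remove a responder. Without a rule for patients who are not rescanned, the Group 1 response count depends partly on which responders the investigator chooses to image again. The same person reads the first scan, knows the treatment, and decides whether the response is tested again.

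Two analysts could also report different rates from the same data. One, working from Section 8.4 alone, would count an unrescanned PR. The other, applying the Appendix 5 table, would not.

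This bears on a secondary endpoint, its lower 80% confidence bound, and the Section 8.3 rule that three or fewer responses among 30 suggest lack of efficacy. At exactly four first-scan responses, a single discretionary rescan that fails to confirm would change the conclusion.

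**Working it through.** **1. The plan's own figures (Section 8.3, n = 30).** With X binomial(30, p):

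- P(X ≤ 3 | p = 0.05) = Σ_{k=0..3} C(30,k) 0.05^k 0.95^(30−k) = 93.9%. The plan states 94%.
- P(X ≥ 4 | p = 0.20) = 87.7%. The plan states 87%.

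Table 8.4 reproduces as exact one-sided bounds, where L(x) is the 0.20 quantile of Beta(x, 31 − x):

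| Responses | Computed | Printed |
|---|---|---|
| 4/30 | 7.8% | 8% |
| 9/30 | 22.1% | 22% |
| 10/30 | 25.1% | 25% |
| 12/30 | 31.3% | 31% |

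The one departure is 1/30 (computed 0.7%, printed 0%), which does not matter here. The efficacy arithmetic is sound. What is undefined is the endpoint that goes into it.

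**2. Effect on an observed rate.** The documents give no confirmation-failure rate. I assume 12 first-scan responses of 30, with 20–25% failing on rescan, and take the reading in which an unrescanned response counts.

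- Nobody rescanned: 12/30 = 40%, bound 31.3%.
- All rescanned, 25% fail: 12 × 0.25 = 3 lost; 9/30 = 30%, bound 22.1%.
- All rescanned, 20% fail: 12 × 0.20 = 2.4, taken as 2 lost; 10/30 = 33%, bound 25.1%.

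The gap is 7 to 10 percentage points. Any partial or selective rescanning falls between these ends, because under this reading a rescan can only remove a response.

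**3. Effect on the four-or-more rule.** Let p be the first-scan response rate, q the share of responders rescanned, and f the share of rescans that fail. With rescanning at random, the counted rate is p(1 − qf). For p = 0.20, q = 1, f = 0.20 this is 0.20 × 0.80 = 0.16, and P(X ≥ 4 | 0.16) = 73.0%. P(4 or more) at a 20% first-scan rate:

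| Rescanned | f = 10% | f = 20% | f = 30% | f = 40% |
|---|---|---|---|---|
| None | 87.7% | 87.7% | 87.7% | 87.7% |
| Half | 84.8% | 81.4% | 77.5% | 73.0% |
| All | 81.4% | 73.0% | 62.1% | 49.3% |

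At a 40% first-scan rate, P(4 or more) is still 95.2% with all rescanned and f = 40%. At 5% it is 6.1% with none rescanned, and 4.4% down to 1.2% with all rescanned over the same range of f.

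**4. Which region is relevant.** Section 1.1.3.1 cites intracranial response rates in symptomatic patients of 16.7% on nivolumab plus ipilimumab (n = 18) and 59% on dabrafenib plus trametinib (n = 17). The sensitive region cannot be dismissed, but the regimen may well lie above it.

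**The case against.** The best defence is that imaging, brain included, already continues every 12 weeks until progression or the end of treatment, whichever is later. Every responder still in follow-up therefore has a later scan at least 4 weeks on, and the discretion governs only an extra, earlier MRI. This stands in part. It makes the none-versus-all comparison an upper limit. It does not close the gap, because the plan never makes the scheduled scan the confirmatory one.

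Three stronger readings are tempting and are not supported:

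- A reader might infer that patients who are not rescanned keep their response. Section 5.3.1 is silent on them, and the Appendix 5 table, if it applied, would deny it.
- A reader might infer that Appendix 5 contradicts Section 5.3.1. Its text is conditional and refers back to the protocol, so the cross-reference is unresolved rather than contradictory.
- A reader might infer that every response rate in the trial is exposed to discretionary rescanning. The clause covers intracranial response, and so bears on Group 1 through Section 3.1. Group 2 has a different gap: no confirmation rule in the body at all.

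It is also fair to say that response is secondary and that Section 8.3 intends the 80% bound to be suggestive only. The clinical benefit rate is less affected, because a cancelled PR may still count as stable disease. These points limit the importance of the problem without removing it.

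**Conclusion.** The concern holds for Group 1 intracranial response. Discretionary rescanning, cancellation when a rescan fails, and no rule for unrescanned responses together let the reported rate depend on imaging practice as well as on treatment.

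The 7 to 10 point gap should not be read as the expected bias. It compares none with all rescanned, rests on an assumed 12/30 and 20–25% failure, and takes unrescanned responses as counted. With scans already scheduled every 12 weeks, it is an upper limit under those assumptions. The four-of-30 rule is materially exposed only when the true rate is near 20%, where the chance of passing falls from 87.7% to 73.0% if all are rescanned and 20% fail. At 40% or more the conclusion hardly moves. The primary DLT endpoint is not touched. This should be corrected, but it does not undermine the design.

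**What to change.** Remove the discretion clause from the definition of response, and apply one rule to every first-scan CR or PR in both compartments:

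- A response is confirmed if CR or PR criteria are met on the first evaluable scan at least 4 weeks later. The next scheduled scan serves when there is no earlier one.
- A response with no later evaluable scan counts as unconfirmed.
- Sections 8.2 to 8.4 should state which version the four-of-30 rule and the lower 80% bound use.
- Report both the confirmed and the unconfirmed rate for all evaluable patients.
- Align Appendix 5 (5.8a) with this rule.

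The cost is wording only, with no extra scans. The confirmed rate will be lower than the unconfirmed one, possibly noticeably where the only later scan is 12 weeks on. As a rough guide, Section 1.1.3.1 cites a median response duration of 22 weeks in a heavily pretreated encorafenib plus binimetinib case series. If durations were exponential, 0.5^(12/22) = 69% would last 12 weeks, so 12/30 would become about 8/30 (27%; Table 8.4 bound 19%). That is why both rates should be reported, and why the rule should accept an earlier scan at 4 weeks or more instead of requiring persistence to 12 weeks.

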5.3.2 Algorithms for Response Assessment

5.3.2.1 Safety

The primary endpoint of the study is safety and tolerability of triple or quadruple therapy and will be assessed in Phase I.

5.3.2.2 Secondary Endpoints – Efficacy

Secondary efficacy endpoints of the study include PFS and ORR in all randomized participants.

5.4 Biomarker Assessments

A variety of factors that could potentially predict clinical response to triplet or quadruple therapy will be investigated in peripheral blood and in tumor specimens. Data from these investigations will be evaluated for associations with response, survival (OS, PFS) and/or safety (AE) data. All samples collected may also be used for future exploratory analyses (unless restricted by local requirements) to assess biomarkers associated with melanoma or immunotherapy treatment. Complete instructions on the collection, processing, handling and shipment of all samples described herein will be provided in a separate Lab Manual.

Biomarkers

Biomarker measures of baseline and on-treatment peripheral blood, serum, and tumor samples will be used to identify pharmacodynamic markers of treatment. Additional biomarkers related to mechanism of action and markers associated with clinical response to encorafenib +/- binimetinib + nivolumab + low dose ipilimumab will be explored.

A detailed description of each biomarker sample analysis and assessment is described below and a schedule of biomarker sample collections is provided in the table. Further details of blood and tissue collection and processing will be provided in the Lab Manual.

Peripheral blood and tumor tissue will be collected prior to therapy and at selected time points on treatment. If a biopsy or surgical resection is performed at the on treatment or at the time of recurrence or suspected recurrence, tumor sample should also be submitted for analysis. If biomarker samples are drawn but study treatment(s) is not administered, samples will be retained. Detailed instructions of the obtaining, processing, labeling, handling, storage and shipment of specimens will be provided in a separate Lab Manual at the time of study initiation.

Study Day of Sample Collection*	Serum ^a	Whole Blood ^a	Tumor Biopsy ^{a,b}	Plasma ctDNA ^a
Screening	X	X	X	X
Prior to dose at week 4	X	X		X
Between week 4-7			X	
At 12 week restaging	X	X		X
At progression	X	X		X

* Protocol specified windows apply to biomarker assessments

^a Instructions for the collection and processing of all samples will be provided in the laboratory manual.

^b Fresh tumor biopsy will only be collected in Phase I

Biomarker Measures

Immunomodulatory properties of encorafenib with and without binimetinib in combination with nivolumab and ipilimumab will be investigated in peripheral blood and tumor samples as detailed below.

Peripheral Blood Studies Peripheral blood samples will be taken prior to initiation of study therapy and on designated time points post-treatment. Above samples will be analyzed for the following measures:

Peripheral Blood Soluble Factors (Serum and Plasma) Baseline and post-treatment modulation of serum levels of chemokines, cytokines and other immune mediators will be assessed by techniques that may include, but are not limited to ELISA, LC-MS.

Immunophenotyping Peripheral blood samples will be taken prior to initiation of study therapy and at designated time points on-treatment. These whole blood or PBMC samples may be used for characterization of the immune cell subsets in the peripheral blood. Analyses may include, but not necessarily be limited to, the proportion of T, B, and NK cells; monocytes and MDSCs as well as their function status measured by Ki67.

Peripheral Blood Genomic and Gene Expression Profiling Peripheral biomarker measures: PBMCs, plasma, serum, or RNA/DNA derived from whole blood may be used for future exploratory analyses such as, but not limited to assessment of gene expression,

Phase I/II study of encorafenib and binimetinib with nivolumab and low dose ipilimumab in metastatic *BRAF* mutant melanoma

tumor mutational burden (TMB), to assess biomarkers of immune cell populations associated with tumor type or therapy.

T Cell Receptor sequencing DNA-derived from whole blood or PBMCs may be used for the assessment of T cell receptor repertoire by genomic sequencing technologies.

Tumor Biopsies and Tumor-Based Biomarker Measures Mandatory tumor biopsy specimens will be obtained at baseline and on-treatment to characterize immune cell populations and expression of selected tumor markers. Study participants should have tumor lesions large enough to undergo repeated biopsies (pre- and on-treatment), excisional or at least obtainment of 4 core biopsy specimens. Pathologic confirmation is strongly encouraged at the time of tumor biopsy to confirm adequate tissue collection and biopsy quality. Participants who undergo biopsy or excision for clinical indications should have any tumor that remains preserved for biomarker analysis. Detailed information for the collection and processing of all samples will be provided in the Lab Manual.

In addition to fresh tumor biopsy, participants are required to submit an archival formalin-fixed paraffin-embedded (FFPE) specimen, if collected prior to the enrollment, if available. The archival tumor tissue sample will be used to compare the expression of putative biomarkers to expression in the fresh tumor biopsy.

The pharmacodynamic effects of encorafenib with and without binimetinib in combination with nivolumab and ipilimumab on intratumoral immune response in biopsy samples will be assessed by gene expression analysis or single cell analysis and calculated as fold change (or percent changes) compared to baseline.

Characterization of tumor microenvironment cell population and immune infiltrates in tumor. The number, frequency, and composition of immune infiltrates within the tumor may be assessed before and after exposure to encorafenib with and without binimetinib in combination with nivolumab and ipilimumab using IHC of the FFPE tumor biopsy specimen. IHC assays may be performed using, but not limited to, the following markers: CD8, CD3, CD15, and PD-L1. The composition of tumor immune infiltrate may be assessed before and after treatment using IHC or multi-plex analysis of the FFPE tumor biopsy specimen. IHC assays may be performed using, but not limited to, the following markers: CD8, CD3, CD15, and PD-L1. Fresh and archival tumor samples may be subjected to correlative gene expression and/or IHC analysis.

Tumor DNA/RNA analysis: Fresh tumor biopsy samples may be evaluated by gene expression analysis using RNAseq, single cell RNA sequencing, qRT-PCR or other relevant techniques to interrogate pharmacodynamic effects, mechanism of action, and/or response or resistance to encorafenib with and without binimetinib in combination with nivolumab and ipilimumab. DNA/RNA derived from tumor tissue may be used for analysis of genomic correlates including but not limited to tumor mutational burden and T cell receptor repertoire.

Other exploratory tumor-based biomarker measures: Tumor tissue or derived RNA/DNA may also be evaluated by LCMS, genetic mutation and rearrangement detection methods, such as genome and/or exome sequencing, and/or quantitative PCR or RT-PCR as part of additional exploratory analyses of putative biomarkers possibly associated with response or resistance to encorafenib with and without binimetinib in combination with nivolumab and ipilimumab.

6. ADVERSE EVENTS

An AE is defined as any new untoward medical occurrence or worsening of a preexisting medical condition in a clinical investigation subject administered study drug and that does not necessarily have a causal relationship with this treatment. An AE can therefore be any unfavorable and unintended sign (such as an abnormal laboratory finding), symptom, or disease temporally associated with the use of study drug, whether or not considered related to the study drug.

The causal relationship to study drug is determined by a physician and should be used to assess all AEs. The causal relationship can be one of the following:

Related: There is a reasonable causal relationship between study drug administration and the AE.

Not related: There is not a reasonable causal relationship between study drug administration and the AE.

The term "reasonable causal relationship" means there is evidence to suggest a causal relationship.

AEs can be spontaneously reported or elicited during open-ended questioning, examination, or evaluation of a subject. (In order to prevent reporting bias, participants should not be questioned regarding the specific occurrence of one or more AEs.)

